**Review Status**

Complete  
 Complete

**Required Safety Committee Reviews** - In addition to the IRB, the following committees must review this submission. Each additional committee has a separate online form that the study team will be required to fill out. All committee applications (IRB plus those listed here) must be completed properly before the 'package' of applications can be submitted. The team may complete these additional forms in any order or at any time prior to submission of the IRB Application. To complete or view these additional committees' forms, click on the links below or exit this application and click on the appropriate button on left side of this submission's Workspace.

Name of Related Submission

*This protocol has no related submissions (RSC, GCRC, IBC, etc)*

You may check the progress of your application at any time by returning to the Workspace of this submission. A detailed history, including notes, dates, and times of events, is provided to you for this purpose.

If a reviewer returns the application to you, you must address their concerns and resubmit the protocol for review to all designated departments. After all departments have reviewed the application, it will automatically be sent to the IRB for review. Changes made to the submission after its approval must be submitted as modifications.

**Click the "Finish" button and then click "Submit Application" in the submission Workspace.**

ID: VIEW4E1B10C500000  
 Name: v2\_Final Page of Application

View: IRB - Add a Team Member

Effects of Early Community Services on Child and Family Development

ClinicalTrials.gov Identifier: NCT04019977

Last updated: July 18, 2023

Statistical Analysis Plan

The principal independent variable will be MFC group (MFC participant/non-participant). The dependent variables of interest will be (a) infant emergency room use and overnight hospital stays; (b) family use of community resources and child care; (c) maternal wellbeing; and (d) quality of the home environment. We will also explore long-term differences between MFC and non-MFC participants in (a) rates of official investigations for child maltreatment and (b) two indicators of early educational achievement: kindergarten readiness scores and rates of kindergarten attendance.

A two-tailed intent-to-treat design analysis will include all randomly assigned families (regardless of actual intervention participation). Ordinary least squares regression models will be used to estimate impact of MFC on continuous and categorical outcomes. Poisson regression models will be used for count variables with skewed distribution. Covariates for all models will include the following: Medicaid status (yes/no) at birth and at 6 months, mother race/ethnicity (nonminority/minority), single parent household (yes/no), birth complications (yes/no) including maternal health conditions affecting the baby, infant injuries from birth trauma, and infant distress. Exploratory moderators will include infant birthweight, family Medicaid status, and mothers' adverse childhood experiences and adult attachment security. All results will be analyzed at the .05 significance level.

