## Justification, Objective, & Research Design

**If you uploaded a separate research protocol document in the 'Research Protocol' page, cite the applicable section and page numbers from that document in the answer boxes below.**

1 \* Describe the purpose, specific aims, or objectives of this research. State the hypothesis to be tested:

The purpose of the current study is to evaluate the effects on early child development of early community services, including a community-wide nurse home visiting program, Maryland Family Connects (MFC) program. We hypothesize that MFC participants will be significantly different than non-MFC participants on the following child and family outcomes: (a) (reduced) infant emergency room use and overnight hospital stays; (b) (increased) family use of community resources and (higher quality) child care; (c) (increased) maternal wellbeing; and (d) (increased) quality of the home environment, including home safety and supportive parenting by both parents. We will also explore long-term differences between MFC and non-MFC participants in (a) rates of official investigations for child maltreatment and (b) two indicators of early educational achievement: kindergarten readiness scores and rates of kindergarten attendance.

2 \* Discuss the research design including but not limited to such issues as: probability of group assignment, potential for subject to be randomized to placebo group, use of control subjects, etc.:

For approximately one year and a half starting July 15, 2019, the [REDACTED] will be conducted in partnership with [REDACTED] and Sinai

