Hospital, both located in Baltimore, MD. For the purposes of this study, Sinai Hospital will serve as the community/catchment area. Nurse home visitors recruit these new mothers while they are still in the hospital/maternity ward. Following Dodge et al. (2013; 2014), when the [REDACTED] officially begins, nurse home visitors will enroll new mothers into MFC every other day only (on odd dates). Those new mothers who are not City residents and/or give birth on an even date will not be offered MFC. They will be considered the "control" group and are expected to access community services as they normally would. [REDACTED] staff will recruit ALL Baltimore City residents who give birth at Sinai Hospital, regardless of odd/even birth date, while they are still in the hospital/maternity ward and with post-discharge outreach. If a mother who gives birth on an odd date declines the MFC program, she will still be recruited into the research study. Given that the effects of MFC are a key study question, and MFC is being provided on a random-assignment basis according to child birthdate, this study follows a RCT design. At the same time, we note that its approach is different than many RCT's, in that prospective research participants are not being explicitly invited to be randomized.

3 \* **Describe the relevant prior experience and gaps in current knowledge. Describe any relevant preliminary data:**  
 While nurse home visiting programs have been shown to be effective in reducing infant injuries and improving outcomes for children and families, Family Connects is the first nurse home visiting program to be implemented on a community-wide scale. Evaluations of the Family Connects Program has been conducted by Dodge and colleagues in Durham, North Carolina (Dodge et al., 2013; 2014), demonstrating positive effects such as reduced infant emergency room use and overnight hospital stays, increased families' use of community resources, and improved family well-being. No randomized controlled trials of Family Connects have occurred outside of North Carolina, however. The proposed study seeks to expand the research on the Family Connects Program and assess its outcomes in a mid-sized, mid-Atlantic city.

4 \* **Provide the scientific or scholarly background, rationale, and significance of the research and how it will add to existing knowledge:**  

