## Sample Size and Data Analysis

**If you uploaded a separate research protocol document in the 'Research Protocol' page, cite the applicable section and page numbers from that document in the answer boxes below.**

1 \* Provide the rationale and sample size calculations for the proposed target population:  
Following guidelines established by Cohen (1988) and using Gpower software (Faul et al., 2009), power analyses estimating at least 0.80 power and a significance level of 0.05 indicated that a sample size of 400 (assuming equal groups) will detect small to medium effects in most of the outcomes of interest. Some outcomes are more exploratory in nature. In addition, it is possible that additional research funding garnered in the course of this study will allow for an increased sample size.

2 \* Provide the plan for data analysis. Include in the description the types of comparisons that are planned (e.g., comparison of means, comparison of proportions, regressions, analysis of variance, etc.), which is the primary comparison/analysis, and how the analyses proposed will relate to the primary purposes of the study:  
The principal independent variable will be MFC group (MFC participant/non-participant). The dependent variables of interest will be (a) infant emergency room use and overnight hospital stays; (b) family use of community resources and child care; (c) maternal wellbeing; and (d) quality of the home environment. We will also explore long-term differences between MFC and non-MFC participants in (a) rates of official investigations for child maltreatment and (b) two indicators of early educational achievement: kindergarten readiness scores and rates of kindergarten attendance.

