The researchers will request permission to contact the mothers when their infants are approximately 6 months old to schedule the in-home or virtual interview assessment. Informed consent will be collected at the time of this assessment. During recruitment, the researchers will also confirm mothers' home address and phone number and share their own contact information. Last, all mothers who agree to be contacted will also receive monthly postcards and text messages providing a "fun fact" about typical infant developmental milestones and monthly text messages to remind them that we will be inviting them to participate in the psychosocial interview around the time of their infant's 6-month birthday. Research staff will copy/paste the monthly text message from the Notes app or manually type in each message. If a mother texts the RA's work cell phone with questions about the study, the RA will respond with the appropriate information (e.g., interview location). In cases where a mother may disclose concerning information (e.g., depressive symptoms), information about mental health resources will be provided. This list will include resources from The [REDACTED] and other appropriate community referrals.

[REDACTED] will not be recruiting from the University of Maryland Baltimore.

We note that without the hospital's ongoing provision of information about their maternity patients, the research could not be practically carried out because we would not be able to identify prospective participants. The hospital has agreed to share this information with the study team.

The [REDACTED] nurse home visitors will be providing information about MFC to eligible mothers upon program recruitment and enrollment whereas the [REDACTED] will be presented as a study of what it's like to raise a baby in Baltimore. Research staff will not discuss MFC directly, as only approximately half of the research participants will have been recruited into MFC. Research staff do not plan to debrief research participants on the impacts of MFC.

**2 \* Describe measures that will be implemented to avoid participant coercion or undue influence (if not applicable to the study, enter "N/A"):**

Research staff will explain to potential participants that participation in the study is completely voluntary and that they may opt out at any time. Participation in the study will not be linked to the services they receive from Sinai Hospital or from any other institution or agency.

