## Potential Benefits and Alternatives

**If you uploaded a separate research protocol document in the 'Research Protocol' page, cite the applicable section and page numbers from that document in the answer boxes below.**

1 \* **Describe the potential direct benefit(s) to participants:**

There are no direct benefits to research participation. Randomly assigned intervention participants are anticipated to benefit from intervention participation.

2 \* **Describe the importance of the knowledge expected to result from the study:**

Family Connects is the first program of its kind to be implemented on a community-wide scale. Family Connects was developed as a brief, universal, postnatal nurse home visiting intervention intended to screen for risk, provide brief intervention, and connect families with more intensive evidence-based services as needed. A primary goal of Family Connects is to reduce the incidence of infant injury and use of emergency medical care in the first year of life. Understanding the feasibility and efficacy of Maryland Family Connects will contribute importantly to the nurse home visiting and community intervention literatures. Findings from this study will also have implications for Maryland infant and maternal health policy.

3 \* **Describe how the potential risks to participants are reasonable in relationship to the potential benefits:**

This is a minimal risk study. The primary risk in this study is that participants may experience some interview questions as intrusive or uncomfortable. As described, however, the research team will provide a list of local mental health resources to all participants. This will offer support to those who may feel uncomfortable, who have disclosed risk of self-harm, childhood maltreatment, have screened positive for depression, or need additional support as a result of their participation in the study.

4 \* **Describe the alternatives to participation in this study. If there are no alternatives, state that participation is voluntary and the alternative is not to participate. For intervention studies, describe appropriate alternative clinical procedures or courses of treatment available to subjects.**

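### The principal variable is labelled by MFC participation, which conflicts with the plan's own intent-to-treat rule; it should be defined as assigned group by birth date

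*SAP*

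**What the plan says.** The SAP names the exposure by its two levels: "The principal independent variable will be MFC group (MFC participant/non-participant". The protocol uses the same words in Sample Size and Data Analysis, item 2.

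The next paragraph of both documents sets the analysis principle: "A two-tailed intent-to-treat design analysis will include all randomly assigned families (regardless of actual intervention participation".

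In Justification, Objective, & Research Design, item 2, the protocol assigns families by the child's birth date. Odd dates are offered MFC and even dates are not. On refusals it says: "If a mother who gives birth on an odd date declines the MFC program, she will still be recruited into the research study". On controls it says: "Those new mothers who are not City residents and/or give birth on an even date will not be offered MFC", and it then calls these mothers the control group.

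The hypothesis in item 1 of that section is again put in terms of participation: "We hypothesize that MFC participants will be significantly different than non-MFC participants on the following child and family outcomes". The exploratory long-term comparisons (maltreatment investigations, kindergarten readiness and attendance) also contrast MFC with non-MFC participants, in both documents.

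**The concern.** Participation cannot be the exposure in an analysis that disregards participation. The two variables do differ in this trial, because the protocol expects some odd-date mothers to decline and keeps them in the sample. Under the stated label such a mother is a non-participant and is grouped with even-date families. Under intent-to-treat she belongs to the group offered MFC.

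At stake is what the principal comparison estimates, for every listed outcome. Odd versus even date is a comparison that the mother does not choose. Participant versus non-participant is partly chosen by her. Mothers who accept a nurse visit may differ from those who refuse in ways that the short covariate list (Medicaid status, race/ethnicity, single-parent household, birth complications) does not capture. The resulting bias could favour or disfavour MFC. A reader of the SAP also cannot tell from the variable's definition which of the two analyses was prespecified.

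**Working it through.** **Comparison of the texts**

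- The stated variable has the levels participant and non-participant (SAP; Protocol, Sample Size and Data Analysis, item 2).
- The stated principle is intent-to-treat with participation disregarded (same places, next paragraph).
- The design assigns by birth date and retains decliners (Protocol, Justification, Objective, & Research Design, item 2).
- No section defines a participant as a mother assigned to, or offered, MFC. No separate as-treated or complier analysis is described.

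The contradiction follows from these four points alone. The arithmetic below only shows how much literal coding could matter.

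**The plan's own figure**

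The protocol gives 400 families in equal groups, significance level 0.05 and power of at least 0.80, for effects described only as small to medium. With 200 per arm and a two-sided test, the detectable difference is (1.96 + 0.84) × √(2/200) = 0.28 SD. This fits the description. No numerical effect size is stated, so the 400 cannot be reproduced exactly.

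**Inputs for the illustration**

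- 200 families per arm (from the protocol) and no true MFC effect.
- Uptake u among odd-date mothers: not stated for this trial. 80% is the earlier trial's rate (Protocol, Supporting Literature); 90% and 100% are shown as a range.
- Acceptor-decliner gap g remaining after the covariates: 0.2 to 0.5 SD, in either direction. This is an assumption; the documents give no figure.

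**Formulas under literal coding**

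- Participants: 200u. Comparison group: 200(1 − u) odd-date decliners plus 200 even-date families, or 200(2 − u) in all.
- Even-date families contain the same share (1 − u) of would-be decliners. The comparison group therefore holds 400(1 − u) decliners or would-be decliners, and the bias is g × 2(1 − u)/(2 − u).
- SE = √[1/(200u) + 1/(200(2 − u))], in SD units.
- Two-sided type I error = P(|Z + bias/SE| > 1.96).

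Worked case, u = 0.80 and g = 0.2: groups 160 and 240; bias = 0.2 × 0.4/1.2 = 0.067 SD; SE = √(1/160 + 1/240) = 0.102; type I error = 10.0%.

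| Uptake | Families moved | Groups | g = 0.2: bias, type I | g = 0.3: bias, type I | g = 0.5: bias, type I |
|---|---|---|---|---|---|
| 80% | 40 | 160 v 240 | 0.067, 10.0% | 0.100, 16.5% | 0.167, 37.2% |
| 90% | 20 | 180 v 220 | 0.036, 6.5% | 0.055, 8.4% | 0.091, 14.8% |
| 100% | 0 | 200 v 200 | 0, 5% | 0, 5% | 0, 5% |

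Coding by assigned date moves no family, has no such bias in this model, and keeps the error at 5%.

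**Imbalance**

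Moving from 200/200 to 160/240 raises the SE only from 0.100 to 0.102. At 0.28 SD, power falls from about 80% to about 78%. Unequal group sizes are therefore not a material harm; the self-selection is.

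**The case against.** The best reply is that the SAP answers the point itself. Intent-to-treat ordinarily means comparison by assigned group, and the parenthesis tells the analyst to ignore participation. On that reading, MFC group is shorthand for the assigned arm. Other text agrees. The protocol ties control status to not being offered MFC. Potential Benefits and Alternatives uses participants for the assigned arm: "Randomly assigned intervention participants are anticipated to benefit from intervention participation". The equal groups in the sample-size statement also fit assignment: 15 July 2019 to 14 January 2021 contains 281 odd and 269 even dates (51% and 49%). The Recruitment section is weaker support: "only approximately half of the research participants will have been recruited into MFC" could mean offered or enrolled.

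A second reply is that the size of the problem rests on outside inputs. The gap is assumed and the 80% uptake belongs to another trial. The Lay Summary expects about half of the sample to have participated in MFC. With half assigned, that implies nearly full uptake, where the two codings coincide; at 80% uptake it would be 0.5 × 0.8 = 40%.

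Much of this stands. Assignment is the probable intent, and a reader who inferred from the label that the trial had chosen an as-treated analysis would go further than the documents allow. What does not stand is that nothing needs changing. The intent-to-treat sentence says which families are included without redefining the exposure, and an as-treated analysis can also include every assigned family. The participation wording recurs in the hypothesis and the long-term comparisons, so it is not an isolated slip. Because the protocol plans for decliners, exactly 100% uptake is unlikely.

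**Conclusion.** The principal independent variable is wrong as written and should be fixed. It is a wording conflict in the definition of the main comparison, and birth-date assignment is the likely intent.

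The harm is conditional: it arises only if an analyst codes the label literally. The figures of 0.07 to 0.17 SD bias and about 10% to 37% type I error also need 80% uptake and a residual gap of 0.2 to 0.5 SD. At 90% uptake the error is 6.5% to 15%. It would be a mistake to infer that this trial's error rate is 37%. That value combines the lower uptake with the largest assumed gap, and the documents establish neither. The textual conflict does not depend on any of these numbers.

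**What to change.** In the SAP and in the protocol's Sample Size and Data Analysis section, item 2, replace the definition with wording such as: *The exposure for all principal analyses is assigned group: eligible Baltimore City residents giving birth at Sinai on an odd date (MFC offered) versus an even date (not offered), regardless of participation.* Label any participant versus non-participant analysis as secondary.

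Then align three places:

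- The hypothesis in Justification, Objective, & Research Design, item 1: families assigned to be offered MFC versus families not offered it.
- The long-term comparison wording in that item, in Sample Size and Data Analysis, item 2, and in the SAP.
- The control-group sentence in Justification, Objective, & Research Design, item 2. It places mothers who are not City residents among the controls, whereas Participant Selection (item 7.1) and the Eligibility criteria exclude them. These must be reconciled, or the new definition will conflict with the design description.

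Rewording the Lay Summary is optional, because its sentence on service participation also covers other community services that are not assigned.

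The cost is a few sentences. No new data are needed, since assigned group follows from the infant's birth date, and the analysis is the intent-to-treat analysis already planned. Dilution of the effect by non-uptake and selection at the 6-month consent are separate matters that this change does not address.
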